#### **5.4 Analysis Plan for Secondary Objectives**

In addition to HAQ DI score, the effect of adalimumab will also be assessed by the secondary outcome measures which are changes to the Short Form 36-Item Health Survey (SF-36) domain scores, EuroQol 5 dimension 3 level (EQ-5D-3L) index, WPAI outcomes, and Patient Treatment Satisfaction Questions at 12 and 24 weeks after the initiation of adalimumab in RA.

- As to the Short Form 36-Item Health Survey (SF-36) domain scores, the Excel Table 4 summarizes the changes in PCS T-score and MCS T-score at 12 and 24 weeks after the initiation of adalimumab; these changes will be summarized as the mean, SD, minimum, maximum, median, 95% confidence interval; and the mean change will be tested with paired t-tests with p-value listed in the table.
- As to the EuroQol 5 dimension 3 level quality of life questionnaire, the Excel Table 5 summarizes the changes in EQ-5D-3L index at 12 and 24 weeks after the initiation of adalimumab; these changes will be summarized as the mean, SD, minimum, maximum, median, 95% confidence interval; and the mean change will be tested with paired t-tests with p-value listed in the table.
- As to the WPAI outcomes, the Excel Table 6 summarizes the changes in percent overall work impairment and percent activity impairment at 12 and 24 weeks after the initiation of adalimumab; these changes will be summarized as the mean, SD, minimum, maximum, median, 95% confidence interval; and the mean change will be tested with paired t-tests with p-value listed in the table.
- Excel Table 7 describes the change in 4 patient satisfaction questions at weeks 12 and 24 after the initiation of adalimumab, in those patients continuing on adalimumab (responder population). These changes will be summarized as number and percentage of each response and compared with Wilcoxon signed rank test shown by p-value1. Satisfaction will also be dichotomized and analyzed over time with Cochran-Armitage test for trends shown by p-value2 in the table.

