Change in HAQ DI score at 24 weeks after the initiation of adalimumab (observed population). This change will be summarized as the mean and 95% confidence interval and will be tested with a paired t-test.

Secondary Endpoint Analysis

- Change in other PROs (SF-36 domain scales, EQ-5D Index, WPAI total lost productivity) at weeks 12 and 24 after the initiation of adalimumab (observed population). These changes will be summarized as the means and 95% confidence intervals and will be tested with paired t-tests.
- Number and percent of patients achieving a clinically meaningful improvement on the HAQ DI, as defined by a -0.22 point improvement or greater, at weeks 12 and 24 after the initiation of adalimumab (observed population).

Additional Secondary Endpoint Analysis

- Change in HAQ DI score at 24 weeks after the initiation of adalimumab (observed population), compared with those patients not continuing on adalimumab (non-observeds). The mean changes in these two groups will be compared using an independent t-test.
- HCRU will be described using number and percentage within each category (number of consultations, number of procedures received, number of surgeries, number of hospitalizations and length of stay, number of concomitant medications)
- Associations between disease severity and PROs
- Associations between change in disease severity and change in PROs

Exploratory endpoint

- Change in patient satisfaction questions at weeks 12 and 24 after the initiation of adalimumab (observed population). These changes will be summarized as number and percentage of each response and compared with Kruskal-Wallis test. Satisfaction will also be dichotomized and analyzed over time with

Cochrane-Armitage test for trends.

Milestones:

Start of Data Collection : 19 Oct, 2015

End of Data Collection : 28 Feb, 2018

Study Progress Report : Not applicable

Interim Report : Not applicable

Registration in the EU PASS Register : Not Applicable

Final Report of Study Results : 31 Aug, 2018

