The main secondary analysis will be summarized as the mean and 95% confidence interval and will be tested with a paired t-test without adjusting for baseline disease severity. For sensitivity analysis, the mean change in HAQ DI at Week 12 will be analyzed using ANOVA adjusting for baseline disease severity.

Other secondary analysis include:

- Change in other patient reported outcomes (SF-36 domain scales, EQ-5D Index, WPAI total lost productivity) at weeks 12 and 24 after the initiation of adalimumab, in those patients continuing on adalimumab (observed population). These changes will be summarized as the means and 95% confidence intervals and will be tested with paired t-tests.
- Number and percent of patients achieving a clinically meaningful improvement on the HAQ DI, as defined by a -0.22 point improvement or greater, at weeks 12 and 24 after the initiation of adalimumab (observed population).

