### **2.2 Secondary Objectives**

- To describe the change in other patient reported outcomes (SF-36 domain scales, EQ-5D-3L index, WPAI total lost productivity) at weeks 12 and 24 after the initiation of adalimumab, in those patients continuing on adalimumab (responder

population). These changes will be summarized as the means and 95% confidence intervals and will be tested with paired t-tests.

- To describe the change in patient satisfaction questions at weeks 12 and 24 after the initiation of adalimumab, in those patients continuing on adalimumab (responder population). These changes will be summarized as number and percentage of each response and compared with Wilcoxon signed rank test. Satisfaction will also be dichotomized and analyzed over time with Cochran-Armitage test for trends.
- To summarize the number and percent of patients achieving a clinically meaningful improvement on the HAQ DI, as defined by a -0.22 point improvement or greater, at weeks 12 and 24 after the initiation of adalimumab, in those patients continuing on adalimumab (responder population).

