### 2.3 Additional Secondary Objectives

- To describe the change in HAQ DI score at 24 weeks after the initiation of adalimumab, in those patients continuing on adalimumab (responder population), compared with those patients not continuing on adalimumab (non-responders). The mean changes in these two groups will be compared using an independent t-test.
- Patient's impression of change in RA at weeks 12 and 24 after the initiation of adalimumab, in those patients continuing on adalimumab (as observed population). Each response will be summarized as number and percentage.
- To summarize the healthcare resource utilization using number and percentage within each category (number of consultations, number of procedures received, number of surgeries, number of hospitalizations and length of stay, number and type of concomitant medications)
- To analyze the associations between disease severity and PROs (HAQ DI, SF-36 domain scales, EQ-5D-3L index, WPAI total lost productivity)
- To analyze the associations between change in disease severity and change in PROs (HAQ DI, SF-36 domain scales, EQ-5D-3L index, WPAI total lost productivity)

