#### 5. STATISTICAL ANALYSIS

##### 5.1 General Considerations

The statistical analysis will be performed using SAS® 9.3 software or a later version (SAS Institute, North Carolina, USA) via SAS Enterprise Guide version 6.1. The statistical results will be displayed using tables, listings and/or graphs for each country. Figures will be performed with SAS®.

Unless otherwise specified, results will be provided as descriptive statistics by country. For categorical measures, data will include the frequency (number of cases [N]) and percentage (%) of total study patients observed in each category. Continuous variables will be described with number of patients with missing observations, mean, standard deviation (SD), median, minimum, and maximum.

The following rules will be followed to define the number of decimal positions to report in study results:

For categorical variables:

- 1 for the percentage.

For most of the continuous variables:

- 1 for the mean, SD, median, minimum, and maximum.
- In continuous variables with low values, 2 decimals for all measures will be reported.

A set of draft table shells (see the document, "AbbVie\_ROCKI\_Tableshell\_V0.2\_2Jan2018.xlsx") will be created in advance to

describe the statistical analysis that will be done to fulfill the objectives of this study. Based on the analysis results the tables will be modified accordingly.

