## 6. LIST OF TABLES AND FIGURES IN EXCEL WORKBOOK

Results of the analysis for this study as outlined above will be summarized using MS Excel tables and will be presented as follows:

Excel Tables / Figures	Description
1	Demographic Characteristics at Baseline
2	Clinical Characteristics at Baseline
3.1	Change in HAQ DI at Weeks 12 and 24 after Initiation of Adalimumab
3.2	Change in HAQ DI at Weeks 24 after Initiation of Adalimumab - Responders VS Non-responders
4	Change in SF-36 Domain Scales at Weeks 12 and 24 after Initiation of

	Adalimumab
5	Change in EQ-5D-3L Index at Weeks 12 and 24 after Initiation of Adalimumab
6	Change in WPAI at Weeks 12 and 24 after Initiation of Adalimumab
7	Change in Patient Satisfaction Questions at Weeks 12 and 24 after Initiation of Adalimumab
8	Post-index Healthcare Resource Utilization - RA Related
9.1	Associations between Disease Severity and PROs
9.2	Associations between Change in Disease Severity and Change in PROs
10	GLM - Modifying Effects on Changes in PROs

Please see the document, "AbbVie\_ROCKI\_Tableshell\_V0.2\_2Jan2018.xlsx" for the full set of table shells.

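### SAP 5.4 tests change in the SF-36 PCS and MCS only, whereas the protocol, SAP 2.2 and the Table 4 title specify the SF-36 domain scales

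*SAP*

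**What the plan says.** **Protocol.** Section 9.7.5 includes among the secondary analyses "Change in other patient reported outcomes (SF-36 domain scales, EQ-5D Index, WPAI total lost productivity", at weeks 12 and 24, summarised by means and 95% confidence intervals and tested with paired t-tests. The abstract has the same item: "Change in other PROs (SF-36 domain scales, EQ-5D Index, WPAI total lost productivity) at weeks 12 and 24". Section 9.1 repeats it, but under the additional secondary heading. Section 9.2.4.7 says that the SF-36 has eight scaled scores.

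**SAP objectives.** Section 2.2 reads "To describe the change in other patient reported outcomes (SF-36 domain scales, EQ-5D-3L index, WPAI total lost productivity) at weeks 12 and 24", again with means, intervals and paired t-tests.

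**SAP analysis text.** Section 5.4 introduces "the secondary outcome measures which are changes to the Short Form 36-Item Health Survey (SF-36) domain scores". The SF-36 bullet below it then says that "the Excel Table 4 summarizes the changes in PCS T-score and MCS T-score at 12 and 24 weeks", with mean, SD, range, median, 95% interval and paired t-test. Section 6 titles the same table "Change in SF-36 Domain Scales at Weeks 12 and 24".

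**SAP scoring.** Section 3.5.1 derives the eight domain scores in Steps 3 to 5. It builds PCS and MCS from them in Step 6, as weighted sums of domain z-scores.

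**WPAI.** In Protocol Appendix G, a patient who worked zero hours (Q4 = 0) is sent past Q5. The percent overall work impairment formula in SAP 3.5.1 uses Q5, and SAP 5.4 tests that score.

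**The concern.** The SF-36 analysis in 5.4 is not the one that the protocol and the SAP's own objective specify. PCS and MCS are not another name for the domain scales: the SAP scores them in a separate step, and two weighted composites can hide opposite or uneven movement among eight domains. A programmer who builds Table 4 from the 5.4 text would deliver a table titled as domain scales that contains no domain scale. The specified secondary outcome would then go unreported, without any stated decision to drop it.

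For WPAI, code that requires Q5 would set a patient absent all week because of RA to missing, although that patient has the largest possible work impairment.

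**Working it through.** **1. Passages side by side**

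| Place | SF-36 quantity for change from baseline |
|---|---|
| Protocol abstract | domain scales, weeks 12 and 24 |
| Protocol 9.7.5 | domain scales, weeks 12 and 24 |
| Protocol 9.1 | domain scales, weeks 12 and 24 (listed as additional secondary) |
| SAP 2.2 | domain scales, weeks 12 and 24 |
| SAP 5.4, opening sentence | domain scores, weeks 12 and 24 |
| SAP 6, Table 4 title | domain scales, weeks 12 and 24 |
| SAP 5.4, SF-36 bullet | PCS and MCS T-scores, weeks 12 and 24 |

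Only the bullet differs, and it is the operative instruction for Table 4.

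**2. Number of tests**

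- Specified: 8 domains × 2 visits = 16.
- In SAP 5.4: 2 summary scores × 2 visits = 4, none on a domain.
- Both sets together: 16 + 4 = 20.

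**3. Cost in false positives.** Protocol 9.7.3 sets every test at two-tailed 0.05. If nothing changed, the expected number of false positives is 4 × 0.05 = 0.2 under 5.4 alone and 20 × 0.05 = 1.0 with the domains added. Neither expectation needs the tests to be independent.

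**4. What a domain test can detect.** Protocol 9.5 enrols 89 with 10% drop-out: 89 × 0.9 = 80.1, so about 80 pairs. By the noncentral t distribution, a two-sided 0.05 paired t-test with n = 80 has 80% power for a mean change of 0.317 SD. The domain tests are therefore workable at the planned size.

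**5. Norms.** Step 5 of SAP 3.5.1 standardises each domain with that scale's own US mean and SD, but prints one pair (83.29094 and 23.75883), possibly as an example.

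- For a single domain the transform is linear, so the paired-t p-value is the same with any pair. The reported T-score change and its interval do depend on it: with the printed SD, 1 point on the 0–100 scale is 10/23.75883 = 0.42 T points.
- PCS and MCS are weighted sums of domain z-scores. Using one pair for all eight scales would change the weighting, and so the p-value.

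**6. WPAI (side point).** With its brackets paired in the usual way, the score is Q2/(Q2+Q4) + (1 − Q2/(Q2+Q4)) × Q5/10.

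- Q2 = 40, Q4 = 0: 1 + 0 × Q5/10 = 1, that is 100% for any Q5.
- Q2 = 0, Q4 = 0: 0/0, undefined.

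The documents do not allow the number of such patients to be derived. Protocol 9.5 assumes 50% employed, so about 80.1 × 0.5 = 40 pairs. Including rather than dropping one whole-week absentee moves the mean change by (c − d)/40, where c is that patient's change and d the mean of the other 39. Assuming c anywhere from −100 to +100 points and d from 0 to −20 points, the extremes are (−100 − 0)/40 = −2.5 and (100 + 20)/40 = +3.0 percentage points.

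**The case against.** **The instruction in 5.4 is explicit.** A reader might infer that the SAP leaves the analyst free to choose between domains and summary scores. It does not: the bullet gives one clear content for Table 4. The defect is a departure from the protocol and SAP 2.2 under a domain label, not an open choice.

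**Draft table shells.** SAP 5.1 says of the shells: "Based on the analysis results the tables will be modified accordingly". A reader might infer that the tested scores could be switched once results are known. The sentence does not say so. The shells are to be made in advance to describe the planned analysis, and the modification may concern only layout or empty categories. The point does not rest on it. The dated shell workbook might already list the domains, which could not be checked; the SAP text would still need to agree.

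**Domains elsewhere in the SAP.** SAP 2.3 plans "To analyze the associations between change in disease severity and change in PROs (HAQ DI, SF-36 domain scales" and so on, and 5.5 gives the regressions. This does not fill the gap, because a regression on change in DAS28 does not supply the mean change, interval and test. Nor is it independent evidence that domain changes will be computed, since 5.4 itself puts the domain label on PCS and MCS.

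**Standing of the outcome.** These are unadjusted secondary comparisons, and Protocol 9.1 ranks them lower than 9.7.5 does. That limits the consequence but does not reconcile the texts.

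**WPAI.** Protocol 9.7.1 defers PRO scoring to the developers' recommendations, and SAP 3.5.5 does so for missing items. Those rules are not in the documents and may already cover a skipped Q5. SAP 3.5.5 also has missing counts reported, and whole-week absentees still answer Q6, so they stay in the activity-impairment test. A reader might infer that the work-impairment result is materially biased. The documents do not show that, since the number affected is unknown.

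**Conclusion.** The SF-36 point holds. As written, SAP 5.4 replaces 16 specified paired analyses of eight domain scales with 4 analyses of two composites, and no passage reconciles the two. Confidence is high on the text, with the reservation that the table shells were not seen. It should be corrected, because a specified secondary outcome would otherwise not be reported. The primary HAQ DI analysis is untouched, and nothing here suggests that the PCS and MCS results would themselves be wrong if each domain is normed with its own values.

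The WPAI remark is an optional clarification held with lower confidence. The 100% score for Q2 > 0 and Q4 = 0 follows from the formula whatever Q5 is. Whether a rule is really lacking depends on developers' guidance not available here.

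**What to change.** In the text of SAP 5.4, and not only in the shells:

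- List all eight SF-36 domain scales for Table 4 at weeks 12 and 24, each with mean change, 95% confidence interval and paired t-test.
- State that each domain is normed with its own scale's mean and SD, as the wording of Step 5 already implies.
- Keep PCS and MCS, labelled as additional.
- State that the domain results are to be read by estimate and interval, since the 16 further p-values are unadjusted.

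Optional, after checking the developers' scoring rules: state that percent overall work impairment is 100%, not missing, when Q2 > 0 and Q4 = 0.

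The cost is a short text change and extra table rows. All items are collected and domain scoring is already described. The rise in expected false positives from 0.2 to 1.0 comes from tests that the protocol already specified, so the change restores the plan.

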As this is a postmarketing observational study, Abbvie is NOT involved in the product supply since the drug is being used according to the approved market label and is to be prescribed by the physician under usual and customary practice of physician prescription. This study is non-interventional and the subjects/investigator will follow the current clinical practice in each site. Not additional task will be required other than current practice to keep the data as “real world data collect.

Primary Endpoint

Change in HAQ DI score at 24 weeks after the initiation of adalimumab(observed population). This change will be summarized as the mean and 95% confidence interval and will be tested with a paired t-test.

Secondary Endpoint Analysis

- Number and percent of patients achieving a clinically meaningful improvement on the HAQ DI, as defined by a -0.22 point improvement or greater, at weeks 12 and 24 after the initiation of adalimumab (observed population).

Additional Secondary Endpoint Analysis

- Change in HAQ DI score at 24 weeks after the initiation of adalimumab (observed population), compared with those patients not continuing on adalimumab (non-observeds). The mean changes in these two groups will be compared using an independent t-test.
- Healthcare resource utilization will be described using number and percentage within each category (number of consultations, number of procedures received, number of surgeries, number of hospitalizations and length of stay, number of concomitant medications)
- Associations between disease severity and PROs
- Associations between change in disease severity and change in PROs

- Change in other patient reported outcomes (SF-36 domain scales, EQ-5D Index, WPAI total lost productivity) at weeks 12 and 24 after the initiation of adalimumab (observed population). These changes will be summarized as the means and 95% confidence intervals and will be tested with paired t-tests.
- Change in patient satisfaction questions at weeks 12 and 24 after the initiation of adalimumab (observed population). These changes will be summarized as number and percentage of each response and compared with Kruskal-Wallis test. Satisfaction will also be dichotomized and analysed over time with Cochrane-Armitage test for trends.

All instruments used in the study are translationally validated for the country language.

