9.7.2 Analyzable population

All subjects who received at least one dose of adalimumab during the study will be included. The main analysis will be conducted on the pooled population, where appropriate, with each individual country analyzed separately as supportive data.

9.7.3**Planned Methods of Statistical Analysis**

All statistical tests will be two-tailed with a significance level of 0.05. Descriptive statistics will be provided. Descriptive analysis will be conducted on all key parameters and presented as mean, standard deviation, minimum, maximum, and median when continuous and as “n” and percent when categorical. Change from adalimumab initiation to 24 weeks will be calculated and evaluated for significant improvements using paired t-tests / ANOVA for parametric and Wilcoxon signed-rank for non-parametric data. Analysis will be also be conducted by severity level (moderate vs severe), disease duration quartile (to compare to prior work) and up to two (2) other subgroups. Cochran-Armitage test of trends or other similar methods may be used to compare categories of subjects.

9.7.4**Primary Endpoint Analysis**

The primary endpoint variable will be the change in HAQ DI score at 24 weeks after the initiation of adalimumab (observed population).

The objective of the primary endpoint analysis will be to demonstrate that treatment with adalimumab improves functioning as measured by the HAQ DI in subjects with RA following treatment initiation. This change will be summarized as the mean and 95% confidence interval and will be tested with a paired t-test.

The primary analysis will be summarized as the mean and 95% confidence interval and will be tested with a paired t-test without adjusting for baseline disease severity. For sensitivity analysis, the mean change in HAQ DI at Week 24 will be analyzed using ANOVA adjusting for baseline disease severity.

9.7.5**Secondary Endpoint Analysis**

The main secondary endpoint variable will be the change in HAQ DI at 12 weeks after the initiation of adalimumab.

The objective of endpoint analysis will be to demonstrate that treatment with adalimumab improves functioning as measured by HAQ DI in subjects with RA compared to baseline.

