9.7.6 Additional Secondary Endpoint Analysis

Additional efficacy analysis includes:

- Change in HAQ DI score at 24 weeks after the initiation of adalimumab, in those patients continuing on adalimumab, compared with those patients not continuing on adalimumab. The mean changes in these two groups will be compared using an independent t-test.
- Healthcare resource utilization will be described using number and percentage within each category (number of consultations, number of procedures received, number of surgeries, number of hospitalizations and length of stay, number of concomitant medications)
- Associations between disease severity and PROs
- Associations between change in disease severity and change in PROs

Exploratory endpoint

Change in patient satisfaction questions at weeks 12 and 24 after the initiation of adalimumab (observed population). These changes will be summarized as number and percentage of each response and compared with Kruskal-Wallis test. Satisfaction will also be dichotomized and analyzed over time with Cochrane-Armitage test for trends.

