### **Patient Treatment Satisfaction Questions**

The patient treatment satisfaction questions were developed de novo for this study and are not considered “validated” questions. There are totally 4 questions asking about the patients’ satisfaction with the following 4 aspects respectively:

1. The way RA treatment improves the morning stiffness in and around the joints.
2. The way RA treatment improves the mobility.
3. The way RA treatment improves the ability to perform daily living requiring fine motor skills.
4. The overall RA treatment.

There are totally 5 responses for each of the question: very satisfied, somewhat satisfied, neither satisfied nor dissatisfied, somewhat dissatisfied, and very dissatisfied.

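### Satisfaction ratings repeated in the same patients are tested with methods for independent groups (Cochran-Armitage, and Kruskal-Wallis in the protocol), which makes the tests conservative and costs power

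*SAP*

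**What the plan says.** The schedule of events (protocol 9.1.1) has every patient answer the satisfaction questions at baseline, Week 12 and Week 24. There are four questions, and SAP 3.5.1 says of the scale: "There are totally 5 responses for each of the question".

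SAP 5.4 restricts the analysis to patients who stay on adalimumab and gives each question two p-values. The ordinal responses are "compared with Wilcoxon signed rank test shown by p-value1". For the binary version: "Satisfaction will also be dichotomized and analyzed over time with Cochran-Armitage test for trends shown by p-value2 in the table". SAP 2.2 names the same pair of tests.

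The protocol differs. Its abstract, 9.1 and 9.7.6 describe the ordinal responses thus: "These changes will be summarized as number and percentage of each response and compared with Kruskal-Wallis test". On the binary version 9.7.6 says: "Satisfaction will also be dichotomized and analyzed over time with Cochrane-Armitage test for trends". Yet protocol 9.7.3, on change from initiation to 24 weeks in general, has change "evaluated for significant improvements using paired t-tests / ANOVA for parametric and Wilcoxon signed-rank for non-parametric data".

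Neither document mentions within-patient correlation or a repeated-measures form of these tests. Neither text says where the five levels are split; the table shells, which are not available here, may.

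**The concern.** Cochran-Armitage and Kruskal-Wallis both compute the null variance as if each group held different people. Only one cohort exists and no grouping factor is named for this endpoint, so the ordered factor is visit and the same patients sit in all three groups. Ratings from one patient are usually positively correlated. A change between visits then varies less than these tests assume, and the p-values come out too large.

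The SAP would therefore print two p-values for the same question that rest on incompatible assumptions, one paired and one not. A non-significant p-value2 could be read as no change in the share of satisfied patients when the test was really running well below 5%. Satisfaction is a secondary objective in the SAP and a secondary variable in protocol 9.3, although the protocol abstract and 9.7.6 call it exploratory.

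**Working it through.** **Inputs from the documents.** Three visits, equally spaced (0, 12 and 24 weeks). Two-sided 5% tests (protocol 9.7.3). 89 patients and 10% drop-out (protocol 9.5), so 89 × 0.9 = 80.1, about 80 completers.

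**The plan's own figures.** Protocol 9.5 reproduces: ((1.645 + 0.842) × 0.5 / 0.21)² = 35.06, so 36; ((1.645 + 0.842) × 25 / 9.9)² = 39.44, so 40; 40 / 0.5 / 0.9 = 88.9, so 89. No power, effect size or correlation is given for the satisfaction tests.

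**Assumptions.** Complete visits and the same correlation rho between any two visits. Rho and the effect sizes are assumed and shown as ranges.

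**Cochran-Armitage, closed form.** With equal numbers per visit and scores −1, 0, 1, the statistic depends only on p24 − p0, the change in the proportion satisfied from baseline to Week 24.

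- Variance the test assumes: 2p(1−p)/n
- True null variance: 2p(1−p)(1−rho)/n
- True size: 2 × (1 − Φ(1.96/√(1−rho))), which does not depend on n
- Power where a valid paired test has 80% (noncentrality 2.80): Φ(2.80 − 1.96/√(1−rho)). At rho = 0.5 this is Φ(2.80 − 2.77), or 51%.

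**Kruskal-Wallis over three visits.** H behaves as (1−rho) × chi-square on 2 df, so the true size is P(chi-square(2) > 5.991/(1−rho)).

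| rho | Cochran-Armitage size | Cochran-Armitage power (paired test 80%) | Kruskal-Wallis size |
|---|---|---|---|
| 0.1 | 3.9% | 77% | 3.6% |
| 0.3 | 1.9% | 68% | 1.4% |
| 0.5 | 0.6% | 51% | 0.3% |

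**Simulation of the trend test** (80 patients, 20,000 runs, rho 0.1 / 0.3 / 0.5):

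- No change: Cochran-Armitage size 3.7% / 1.8% / 0.5%; paired test 5.1% / 5.2% / 5.1%.
- 42% to 58% satisfied: Cochran-Armitage power 52% / 53% / 53%; paired test 56% / 68% / 81%.
- 35% to 65% satisfied: 97.6% / 98.7% / 99.5% against 98.1% / 99.6% / 100%.

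A hand check of the middle case uses p = 0.5 and n = 80. The assumed standard error is √(2 × 0.25 / 80) = 0.079, so z = 0.16 / 0.079 = 2.02, barely above 1.96, and power is a little over 50% whatever rho is. A paired test at rho = 0.5 has standard error 0.079 × √0.5 = 0.056 and z = 2.86, so its power is about 81%. The loss is thus precision that pairing would have supplied.

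**Simulation of both tests** (80 patients, five-level ratings, top two levels counted as satisfied, 40% / 48% / 52% satisfied over the visits, latent correlation 0.3 / 0.5 / 0.7):

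- Cochran-Armitage 30% / 28% / 25%, within-patient trend test 38% / 45% / 56%.
- Kruskal-Wallis 30% / 25% / 17%, Friedman 42% / 55% / 75%.

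With a large shift (40% / 64% / 74%), every test has at least 99% power.

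**The case against.** The strongest reply is that little is at stake. Under positive correlation the error is conservative. The SAP's p-value1 is already a paired test of the same responses. The questions are described as not validated, and no sample size rests on them. Protocol 9.7.1 makes the approved SAP govern, so Kruskal-Wallis may never be run. All of this stands, and it limits the consequence. It does not make p-value2 the right test, and the protocol still names a different test from the SAP.

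A second reply concerns the size of the loss. The baseline rating is about earlier therapy and the Week 24 rating is about adalimumab, so their correlation could be low. This is fair. In a simulation with that correlation near 0.1 (80 patients), the size was 3.5% and power for 42% to 58% was 52% against 57%; near zero it was 52% against 54%. The 0.5 figures are the upper end of the assumed range and not a forecast. Equally, protection against false positives depends on the sign: the closed form gives 6.2% at rho = −0.1 and 7.4% at −0.2. Negative correlation is less natural for repeated ratings by one patient, but a paired test removes the question.

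A third reply is that the protocol never names the Kruskal-Wallis grouping factor, and 9.7.3 mentions other groupings such as severity. Visit remains the natural reading, because the sentence concerns change at Weeks 12 and 24 in one cohort. Protocol 9.7.3 also allows methods similar to Cochran-Armitage for comparing categories of subjects, but that does not specify a paired test here.

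**Conclusion.** The point holds. In the SAP it affects p-value2 only; in the protocol it affects both tests named for satisfaction. For correlations of 0.1 to 0.5 the true size of the trend test falls from the nominal 5% to between 3.9% and 0.6%. For a moderate change (42% to 58% satisfied, 80 completers) the loss runs from about 4 points of power (52% against 56%) to about 28 (53% against 81%). For a large change it is negligible. These figures rest on an assumed common positive correlation and complete visits.

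Under positive correlation a significant p-value2 can still be believed; a non-significant one says less than it appears to. The missing cut-point is a lesser gap, which the table shells may fill. This should be corrected before the analysis is run, but it does not threaten the study's main result.

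**What to change.** - **SAP 2.2 and 5.4, p-value2:** replace Cochran-Armitage with a logistic GEE, with visit as a score and patient as the cluster. If a trend is not needed, use McNemar tests of Week 12 and Week 24 against baseline. That gives two comparisons per question instead of one, eight over the four questions, and no longer tests a trend.
- **Cut-point:** state it in the text, for example very or somewhat satisfied against the other three levels.
- **Protocol abstract, 9.1 and 9.7.6:** replace Kruskal-Wallis with Wilcoxon signed-rank, in line with the SAP and protocol 9.7.3, and replace Cochran-Armitage as in the SAP.

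The cost is a few sentences in five places and standard SAS code. No further data or visits are needed.
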